4.5 SUBJECT DISCONTINUATION

Subjects have a right to withdraw from the study at any time.

The subject may be withdrawn from the study for any reasons: if it is in the best interest of the subject, intercurrent illness, adverse events, or worsening condition. [name] may request the withdrawal of a subject because of protocol violations, administrative reasons, or any other valid and ethical reasons.

If a subject discontinues from the study, he or she will not be allowed to re-enter the study.

Reasons for subject discontinuation may include, but are not limited to, the following:

- Sensory rhegmatogenous retinal detachment or Stage 3 or 4 macular hole
- Investigator determination that it is not in the best interest of the subject to continue participation
- Pregnancy
- Endophthalmitis
- Need for anti-VEGF therapy other than ranibizumab in the study eye, unless as a part of the prospective investigational study design
- SAE
- Any other safety concerns

In the event of an adverse event in the study eye that is considered by the investigator to be severe in intensity, serious consideration should be given to discontinuing the subject from the study.

4.7 STUDY DISCONTINUATION

This study may be terminated by **Vitreo-Retinal Associates** or Genentech at any time. Reasons for terminating the study may include the following:

- The incidence or severity of adverse events in this or other studies indicates a potential health hazard to subjects
- Subject enrollment is unsatisfactory
- Data recording is inaccurate or incomplete

4.8 STATISTICAL METHODS

4.8.1 Analysis of the Conduct of the Study

There is no formal sample size calculation in a pharmacokinetic/pharmacodynamics study of this size. A sample size of 10 patients is chosen, making sure that it is feasible financially to conduct the study and logically to complete the study within **6 months**.

4.8.2 Safety Analyses

Any adverse events, laboratory assessments, physical examinations, vital signs, ocular examinations and measurements from all 10 subjects will be utilized to summarize safety data for this pilot study.

4.8.3 Efficacy Analyses

a. Primary Endpoint

Aqueous cytokines and VEGF will be measured with an aqueous tap before the first and after the fourth Lucentis injection.

b. Secondary Endpoints

ETDRS vision will be measured at each visit along with spectral domain OCT.

After the fourth Lucentis injection, the patient will be exited from the study. The patients will continue to receive anti VEGF injections for DME based on clinical need. [name], [name], [name], and [name] will continue to follow all patients

4.8.4 Missing Data

Analyses of efficacy and safety will be based on available cases, without imputation for missing values.

4.8.5 Interim Analyses

No formal schedule of interim analyses is planned. Reports of adverse events from this study may be reviewed and summarized periodically while the study is ongoing to ensure the safety of subjects.

4.9 DATA QUALITY ASSURANCE

Accurate, consistent, and reliable data will be ensured through the use of standard practices and procedures.

5. ASSESSMENT OF SAFETY

Specification of Safety Variables

Safety assessments will consist of monitoring and reporting adverse events (AEs) and serious adverse events (SAEs) per protocol. This includes all events of death, and any study specific issue of concern.

5.1 ADVERSE EVENTS

An AE is any unfavorable and unintended sign, symptom, or disease temporally associated with the use of an investigational medicinal product (IMP) or other protocol-imposed intervention, regardless of attribution.

This includes the following:

- AEs not previously observed in the subject that emerge during the protocol-specified AE reporting period, including signs or symptoms associated with DME that were not present prior to the AE reporting period.
- Complications that occur as a result of protocol-mandated interventions (aqueous taps) will be immediately reported to the IRB.
- If applicable, AEs that occur prior to assignment of study treatment associated with medication washout, no treatment run-in, or other protocol-mandated intervention
- Preexisting medical conditions (other than the condition being studied) judged by the investigator to have worsened in severity or frequency or changed in character during the protocol-specified AE reporting period.

5.2 SERIOUS ADVERSE EVENTS

An AE should be classified as an SAE if the following criteria are met:

- It results in death (i.e., the AE actually causes or leads to death).
- It is life threatening (i.e., the AE, in the view of the investigator, places the subject at immediate risk of death. It does not include an AE that, had it occurred in a more severe form, might have caused death.).
- It requires or prolongs inpatient hospitalization.
- It results in persistent or significant disability/incapacity (i.e., the AE results in substantial disruption of the subject's ability to conduct normal life functions).
- It results in a congenital anomaly/birth defect in a neonate/infant born to a mother exposed to the IMP.
- It is considered a significant medical event by the investigator based on medical judgment (e.g., may jeopardize the subject or may require medical/surgical intervention to prevent one of the outcomes listed above).

5.3 METHODS AND TIMING FOR ASSESSING AND RECORDING SAFETY VARIABLES

The investigator is responsible for ensuring that all AEs and SAEs that are observed or reported during the study are collected and reported to the FDA, appropriate IRB(s), and Genentech, Inc. in accordance with CFR 312.32 (IND Safety Reports).

Adverse Event Reporting Period

The study period during which all AEs and SAEs must be reported begins after informed consent is obtained and initiation of study treatment and ends 30 days following the last administration of study treatment or study discontinuation/termination, whichever is earlier. After this period, investigators should only report SAEs that are attributed to prior study treatment.

Assessment of Adverse Events

All AEs and SAEs whether volunteered by the subject, discovered by study personnel during questioning, or detected through physical examination, laboratory test, or other means will be reported appropriately. Each reported AE or SAE will be described by its duration (i.e., start and end dates), regulatory seriousness criteria if applicable,

suspected relationship to the 0.3mg Lucentis (see following guidance), and actions taken.

To ensure consistency of AE and SAE causality assessments, investigators should apply the following general guidelines:

Yes

There is a plausible temporal relationship between the onset of the AE and administration of the Lucentis or aqueous tap, and the AE cannot be readily explained by the subject's clinical state, intercurrent illness, or concomitant therapies; and/or the AE follows a known pattern of response to the {study drug}; and/or the AE abates or resolves upon discontinuation of 0.3mg Lucentis or dose reduction and, if applicable, reappears upon re-challenge.

No

Evidence exists that the AE has an etiology other than the 0.3mg Lucentis (e.g., preexisting medical condition, underlying disease, intercurrent illness, or concomitant medication); and/or the AE has no plausible temporal relationship to 0.3mg Lucentis administration (e.g., cancer diagnosed 2 days after first dose of study drug).

Expected adverse events are those adverse events that are listed or characterized in the Package Insert or current Investigator Brochure.

Unexpected adverse events are those not listed in the Package Insert (P.I.) or current Investigator Brochure (I.B.) or not identified. This includes adverse events for which the specificity or severity is not consistent with the description in the P.I. or I.B. For example, under this definition, hepatic necrosis would be unexpected if the P.I. or I.B. only referred to elevated hepatic enzymes or hepatitis.

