2.2 Secondary Objectives

3. STUDY DESIGN

3.1 DESCRIPTION OF THE STUDY

Lucentis injections are the current standard of care for diabetic macular edema. The only deviation from the standard of care in the current protocol is an aqueous tap before the first Lucentis injection and the fourth Lucentis injection for diabetic macular edema. Such an approach has been shown to be extremely low risk for the patient. In a study from Pfahler et. al, (5), with 578 vitreous taps there were minimal complications. Vitreous taps are considered riskier than aqueous taps.

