3.3 SAFETY PLAN

A current IRB exists with [name] lab at MSU to analyze vitreous specimens. See attached. The study is funded by Genentech, and an IRB will be obtained for the current protocol and material transfer agreement will be consummated with [name] to send the aqueous samples directly to her lab.

Safety concerns, the only deviation from current standard of care in the current protocol is an aqueous tap before the first Lucentis injection and before the fourth Lucentis injection. We have previously conducted a clinical trial similar to this with the Van Andel Institute for macular degeneration without any complications. Furthermore, Pfahler (5) performed more than 578 vitreous taps without significant morbidity, which are considered riskier than aqueous taps. Compachairo et al (7) performed aqueous taps on 59 patients receiving Lucentis without morbidity. This is six times the number of patients proposed in this clinical trial.

3.5 compliance with Laws and Regulations

This study will be conducted in accordance with current U.S. Food and Drug Administration (FDA) Good Clinical Practices (GCPs), and local ethical and legal requirements.

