4. MATERIALS AND METHODS

4.1 SUBJECTS

4.1.1 Subject Selection

Ten patients will be selected with diabetic macular edema using entry criteria from DRCR protocol T.

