4.5 STUDY ASSESSMENTS

4.5.1 Assessments during the Treatment Period

Patients will be seen once per month, see attached study flow sheet. At visit 0 and at 3 month visit patient will also have an aqueous tap prior to Lucentis injection.

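### The adverse event reporting period in 5.3 opens only at the first ranibizumab injection, so the interval between the first aqueous tap and that injection falls outside it, in conflict with 5.1

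*Combined protocol and SAP*

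**What the plan says.** Section 5.3, under Adverse Event Reporting Period, states that mandatory reporting "begins after informed consent is obtained and initiation of study treatment and ends 30 days following the last administration of study treatment". An earlier end applies if the study is discontinued or terminated first. Only the start is at issue here. Two conditions must both be met: consent, and initiation of study treatment.

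Section 4.3 (Study Treatment) describes ranibizumab and nothing else. Section 4.5.1 fixes the order within the visit: "At visit 0 and at 3 month visit patient will also have an aqueous tap prior to Lucentis injection". Appendix A puts consent, aqueous sample and injection all on Day 1. The Safety Plan (numbered 3.3 in the body) says that "the only deviation from current standard of care in the current protocol is an aqueous tap before the first Lucentis injection", together with a second tap before the fourth injection.

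Other text points the other way. The AE definition in 5.1 extends to protocol-imposed interventions. Its list includes, where applicable, "AEs that occur prior to assignment of study treatment associated with medication washout, no treatment run-in, or other protocol-mandated intervention". A further bullet sends aqueous tap complications to the IRB at once. The opening sentence of 5.3 makes the investigator responsible for collecting all events seen or reported in the course of the study and for reporting them to the FDA, the IRB and Genentech. It sets no treatment-start condition.

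**The concern.** The tap is the one procedure that the protocol adds to standard care, so harm from the tap is the main added risk that the trial can document. A start rule tied to the first injection opens the period after half of the planned taps have been done. The events left out are the immediate ones, including any that lead to the injection not being given. For a patient in that position the period never opens.

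Site staff deciding whether an event must be recorded and sent on are likely to apply the specific period in 5.3 rather than the general sentence above it. They could then report a Day 1 tap event to the IRB under 5.1 and treat it as outside mandatory reporting to the FDA and Genentech.

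**Working it through.** The plan states no figure on this point, so there is none to reproduce. The check is a count and a comparison of sections.

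**Count**

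- Patients: 10 (4.1.1: "Ten patients will be selected with diabetic macular edema using entry criteria from DRCR protocol T").
- Taps per patient: 2, at visit 0 and month 3 (4.5.1).
- Planned taps: 10 × 2 = 20.
- Taps before the first injection: 10 × 1 = 10, and 10/20 = 50%.
- Taps before the period opens if it starts at signed consent: 0 of 20.

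The second tap does not alter this count. Section 3.1 has "an aqueous tap before the first Lucentis injection and the fourth Lucentis injection for diabetic macular edema", whereas 4.8.3 has "Aqueous cytokines and VEGF will be measured with an aqueous tap before the first and after the fourth Lucentis injection". These disagree about the fourth injection, but on either reading the second tap comes long after the first injection.

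**What the 50% measures**

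It is the share of taps that have an interval outside the period. It is not the share of complications. Tap and injection share the Day 1 visit, which gives three cases:

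- Onset after the first tap but before the injection: outside the period.
- Onset after the injection, even if caused by the tap: inside.
- Patient tapped but never injected: every event outside, because treatment is never initiated.

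Let f be the proportion of first-tap complications in the first or third case. The documents give neither the tap-to-injection interval nor a tap complication rate. So f could lie anywhere from 0 to 1, and the text does not narrow it.

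**Sections side by side**

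| Section | Event starting between first tap and first injection |
|---|---|
| 5.1, AE definition and pre-treatment bullet | Counts as an AE |
| 5.1, tap bullet | Immediate report to the IRB, no start condition |
| 5.3, opening sentence | Collect and report to FDA, IRB and Genentech |
| 5.3, reporting period | Outside mandatory reporting |
| 5.6.2(i), transmission paragraph | Covers SAEs and events of special interest in patients exposed to the product; a patient not yet injected is not exposed |
| 5.6.5, expedited FDA reports | Depend on possible relation to Lucentis |
| 4.8.2, safety summary | Uses any adverse events from all 10 subjects; does not invoke the period |

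The IRB bullet is therefore the only route that names tap complications and carries no qualification. The contradiction lies between the start clause in 5.3 on one side and 5.1 with the opening sentence of 5.3 on the other. The exposure wording in 5.6.2(i) adds to it for a patient not yet injected.

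**The case against.** The strongest reply is that one clause is outweighed by several. Section 5.1 defines these events as AEs and requires immediate IRB notice. The first sentence of 5.3 covers events during the study. The affirmative causality text in 5.3 names the aqueous tap. Section 5.6.2(i) opens by requiring all SAEs to go to Genentech. AEs are described by start and end dates, not clock times, so a Day 1 tap event would carry the same date as the first injection and would probably be recorded.

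Much of this stands. It shows that loss is not certain, and that for a patient who is injected the gap may have little practical effect. It does not remove the contradiction, and it does not help where no injection follows. It is also possible to read study treatment as including the tap, but 4.3 gives that reading little support.

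A reader might infer three stronger things that the documents do not support:

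- *That all complications of the 10 first taps go unreported.* Those starting after the injection are inside the period, and tap complications go to the IRB in any case.
- *That the safety summary must understate tap risk.* Section 4.8.2 takes any adverse events from all 10 subjects and is not limited to the 5.3 period or to injected patients. Understatement would follow only if collection itself fell short.
- *That the gap invalidates a per-tap rate or confidence limit.* The plan promises neither; 4.8.2 is descriptive. Upper limits computed for 10 or 20 taps would answer a claim that the plan does not make.

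**Conclusion.** Wrong as written: an internal contradiction, moderate priority. The stated start of the reporting period excludes the interval from first tap to first injection at 10 of 20 planned taps (50%), and all events in any patient tapped but never injected. The consequence is a risk of incomplete collection and of incomplete reporting to the FDA and Genentech. How many events are affected cannot be calculated.

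The conclusion rests on two readings: that study treatment means ranibizumab, as in 4.3, and that both start conditions in 5.3 must be met, as the wording says. It does not touch the VEGF, cytokine or clinical-response objectives.

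**What to change.** 1. In 5.3, start the AE and SAE reporting period at signed informed consent and delete the treatment-initiation condition. This brings it into line with 5.1 and with the opening sentence of 5.3.
2. In 5.6.2(i), make clear that the reference to product exposure does not exclude tap events in a patient not yet injected.

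Section 4.8.2 needs no change for this purpose. The expedited FDA criteria in 5.6.5 turn on relation to Lucentis and are not altered by moving the start date, so the fix should not be described as making every tap event an expedited report.

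The cost is a sentence in each of two sections, plus a few minor events between consent and injection that will now be recorded. No treatment or visit changes.

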4.5.2 Early Termination Assessments

Subjects who withdraw from the study prior to completion should return for an early termination evaluation **10 days ($\pm X$ days)** following the last injection/study visit for monitoring of all adverse events (serious and

nonserious). The schedule of assessments for early termination is the same as that for the final visit.

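### Reporting of all AEs (5.3) can close 8 to 10 days before the early-termination visit (4.5.2) that is meant to monitor all AEs

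*Combined protocol and SAP*

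**What the plan says.** Section 5.3 (Adverse Event Reporting Period) sets the period in which every AE and SAE must be reported. Its start is defined first: the period "begins after informed consent is obtained and initiation of study treatment". The closing rule, on which this point turns, is that the same period "ends 30 days following the last administration of study treatment or study discontinuation/termination, whichever is earlier". The next sentence limits what follows: "After this period, investigators should only report SAEs that are attributed to prior study treatment".

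Section 4.5.2 (Early Termination Assessments) provides one further visit: "Subjects who withdraw from the study prior to completion should return for an early termination evaluation 10 days", with the tolerance left as the placeholder X. The 10 days are counted "following the last injection/study visit for monitoring of all adverse events", and the text makes clear that serious and nonserious events are both meant.

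On visit spacing, section 4.5.1 says "Patients will be seen once per month, see attached study flow sheet". The flowchart in Appendix A shows Day 1 and Weeks 4, 8 and 12, with an injection at each. The section headed Subject Discontinuation lets a subject withdraw at any time. No section extends the reporting period to the early-termination visit.

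**The concern.** The early-termination visit exists to pick up all AEs in subjects who leave early. If the reporting period has already closed when that visit takes place, the visit is required but part of what it finds no longer has to be reported.

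The closure also affects what counts as an AE. Section 5.1 lists new AEs as those that arise within the protocol-specified reporting period, and section 5.6.2(b) ties the reporting of deaths regardless of attribution to the same period. A non-serious event that starts after closure therefore falls outside both the listed category and the duty to report.

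Withdrawal for safety is foreseen. The Subject Discontinuation section asks that discontinuation be seriously considered "In the event of an adverse event in the study eye that is considered by the investigator to be severe in intensity". Section 4.8.2 bases the safety summary on all 10 subjects, so each withdrawn subject is one tenth of it.

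**Working it through.** The plan gives no figure of its own here, so the check is date arithmetic.

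**Inputs.** Day 0 is the last injection; one always exists, because the period starts only once treatment has begun. Let d be the day of the withdrawal visit. The flowchart spacing gives d = 28 for a subject withdrawn at the next scheduled visit before dosing. The early-termination evaluation is on day d + 10 (4.5.2, counted from the study visit). Counting from the injection would put it on day 10, already past at a day-28 withdrawal.

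**Two readings of the closing rule in 5.3.**

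- Reading A: the 30 days apply to both dates. Closure = min(0 + 30, d + 30) = day 30. The last dose cannot come after discontinuation, so the discontinuation date never governs.
- Reading B: the 30 days apply only to the last dose, and discontinuation itself closes the period, dated at withdrawal. Closure = min(30, d).

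**Results.** Gap = evaluation day minus closure day; a positive gap means that the evaluation is outside the period.

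| Withdrawal visit d | Evaluation | Closure A | Gap A | Closure B | Gap B |
|---|---|---|---|---|---|
| 0 (dosed at that visit) | 10 | 30 | none | 0 | 10 |
| 14 (unscheduled) | 24 | 30 | none | 14 | 10 |
| 20 (unscheduled) | 30 | 30 | 0 | 20 | 10 |
| 21 (unscheduled) | 31 | 30 | 1 | 21 | 10 |
| 28 (scheduled, not dosed) | 38 | 30 | 8 | 28 | 10 |
| 31 (longest calendar month) | 41 | 30 | 11 | 30 | 11 |

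Under Reading A a gap needs d + 10 > 30, that is d > 20. Under Reading B it arises for any d, including withdrawal at a dosed visit. The scheduled undosed visit fails under both.

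**Visit tolerance.** For d = 28 the evaluation could fall within the period only if X were at least 8 days (A) or 10 days (B). X is not filled in.

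**Test of a one-word change.** With *later* in place of *earlier* and d = 28, Reading A closes on max(30, 58) = day 58, which covers day 38. Reading B closes on max(30, 28) = day 30, still 8 days before the evaluation. The one word is enough only under Reading A.

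**The case against.** **The gap is narrow.** Under Reading A a subject withdrawn at a dosed visit, or within 20 days of the last dose, is unaffected. Reading B depends on dating discontinuation at withdrawal, which the documents do not define. Section 4.5.2 gives the early-termination visit the final-visit schedule, and Appendix A puts study exit at the final visit. If discontinuation is dated at that evaluation, closure is min(30, d + 10), and again only d > 20 is affected. Both points stand, but the day-28 case survives each of them.

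**Other sections catch much of what matters.** Section 5.6.2(i) requires SAEs, including unrelated ones, and events of special interest to be sent for exposed patients, and it states no window. Section 5.6.2(f) covers attributed SAEs after the study, and 5.1 sends complications of the aqueous tap to the IRB at once. This largely stands. It narrows the loss to new-onset non-serious AEs, plus unattributed SAEs to the extent that 5.3 overrides 5.6.2(i), which the protocol does not settle.

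**Collecting is not reporting.** Section 4.5.2 itself requires all AEs to be monitored at the visit, 5.6.1 wants AEs elicited at every evaluation, and 4.8.2 summarises any AEs without naming a window. A sponsor could fairly include these events. But the specific closing rule in 5.3 says otherwise, and staff following it would be within the protocol if they left them out.

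**Stronger inferences that the documents do not support.**

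- A reader might infer that reporting stops first for subjects with the worst events, so that the profile looks too benign. Under Reading A everyone has the same 30 days after the last dose. The event that prompts withdrawal normally starts inside the period and stays reportable.
- A reader might infer that closure prevents the AE end date that 5.3 asks for. The period limits which events must be reported, not follow-up of those already reported; 5.6.2(i) and 5.6.4 ask for follow-up information as it becomes available.
- A reader might use the 7-8 day half-life in 1.4.1 to argue that much of the dose is still in the eye at closure. In the worked case, assuming first-order loss, 0.5^(28/7) to 0.5^(28/8) is 6% to 9% on day 28, and 0.5^(38/7) to 0.5^(38/8) is 2% to 4% on day 38. The conflict does not rest on these figures.

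**Conclusion.** Sections 4.5.2 and 5.3 contradict each other for a subject withdrawn undosed at a scheduled visit. The evaluation for all AEs falls on day 38, which is 8 days after closure (Reading A) or 10 days after it (Reading B). With calendar-month spacing of 31 days the gap is 11 days under either reading. Reading B, if discontinuation is dated at withdrawal, also puts evaluations after a dosed visit outside the period.

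This rests on counting the 10 days from the study visit and on an unfilled tolerance. How often it would happen cannot be estimated, because the plan gives no withdrawal rate. The consequence is possible incompleteness of the AE data, mainly new non-serious events in the gap. It is worth correcting because the contradiction is plain and the correction cheap. The documents do not show a bias in the safety summary, and the primary endpoint is not touched.

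**What to change.** In section 5.3:

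1. State whether the 30 days apply to both the last administration and discontinuation/termination, or only to the last administration.
2. Replace *earlier* with *later* in the closing rule.
3. Add that in every case the period runs at least through the early-termination evaluation of 4.5.2.

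The third change removes the conflict under either reading; the first two make the rule clear for everyone else.

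The cost is one word and two short statements. Recording lasts slightly longer for withdrawn subjects, and no visit is added, because the early-termination evaluation is already required.

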5.6 PROCEDURES FOR ELICITING, RECORDING, AND REPORTING ADVERSE EVENTS

5.6.1 Eliciting Adverse Events

A consistent methodology for eliciting AEs at all subject evaluation time points should be adopted. Examples of non-directive questions include:

- “How have you felt since your last clinical visit?”
- “Have you had any new or changed health problems since you were last here?”

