6.2 STUDY COMPLETION

The following data and materials are required by Vitreo-Retinal Associates before a study can be considered complete or terminated:

- Laboratory findings, clinical data, and all special test results from screening through the end of the study follow-up period (if applicable)

- Case Report Forms properly completed by appropriate study personnel and signed and dated by the investigator (if applicable)
- Copies of protocol amendments and IRB approval/notification (if applicable)
- A summary of the study prepared by the Principal Investigator (will accept IRB summary close letter) (if applicable)
- All regulatory documents (e.g., curricula vitae for each Principal Investigator, U.S. FDA Form 1571 and 1572)

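### Completers leave the study at the visit of their second aqueous tap, so no scheduled adverse-event contact falls in the 30 days that follow it

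*Combined protocol and SAP*

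**What the plan says.** **Timing of the taps and exit.** Section 4.5.1 states: "At visit 0 and at 3 month visit patient will also have an aqueous tap prior to Lucentis injection". Section 4.8.3 states: "After the fourth Lucentis injection, the patient will be exited from the study". The Appendix A flowchart has four columns (Day 1, Week 4, Week 8, Week 12) and marks the aqueous sample, the Lucentis injection and Study Exit together at Week 12.

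**After exit.** Section 4.8.3 continues: "The patients will continue to receive anti VEGF injections for DME based on clinical need". It adds that the treating physicians go on following every patient. It gives no date for a next visit and no AE collection.

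**AE window and elicitation.** Under section 5.3 the reporting period "ends 30 days following the last administration of study treatment or study discontinuation/termination, whichever is earlier". Section 5.6.1 ties active questioning to visits: "A consistent methodology for eliciting AEs at all subject evaluation time points should be adopted".

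**Early withdrawals.** Section 4.5.2 asks patients who withdraw before completion to return about 10 days (the tolerance is left unfilled) "following the last injection/study visit for monitoring of all adverse events", with the same assessments as the final visit.

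**Tap-related provisions.** The Safety Plan (numbered 3.3 in the body) identifies the tap as the protocol's sole departure from standard care. Section 5.1 sends tap complications to the IRB at once. In section 5.3, the rule for answering *Yes* on causality names the tap alongside Lucentis, while the rule for *No* names Lucentis only. Section 5.6.2(f), on serious events after study participation, also names Lucentis only.

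**The concern.** The protocol defines a 30-day period in which AEs must be reported, but for completers it schedules nothing in that period at which they would be asked about or looked for. The gap falls on the procedure that the study itself adds. It is also uneven: someone who drops out after one injection is recalled for an AE check, while someone who stays to the end and has a second tap is not, and no reason is given.

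At stake is the completeness of the safety summary in section 4.8.2. A non-serious or late-appearing event after the second tap would enter it only if the patient volunteered it or routine care recorded it and someone passed it to the study. Completeness would then differ between first and second taps for reasons unrelated to the taps.

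**Working it through.** The plan states no figure that can be recomputed here: the 30 days is a rule, and section 4.8.1 says there is no formal sample size calculation. The check is a count against the schedule.

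**Inputs**
- Patients: 10 (sections 4.1.1 and 4.8.1). All are assumed to complete.
- Visits: Day 1, Weeks 4, 8 and 12 (Appendix A), taken as days 0, 28, 56 and 84 after the first injection.
- Taps: days 0 and 84. Injections: days 0, 28, 56 and 84.
- Window after the last treatment: 30 days (section 5.3), so day 84 + 30 = day 114.

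**Step 1. Scheduled contacts in the 30 days after each procedure**

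| Procedure | Day | Next scheduled contact within 30 days |
|---|---|---|
| Tap 1, injection 1 | 0 | day 28 |
| Injection 2 | 28 | day 56 |
| Injection 3 | 56 | day 84 |
| Tap 2, injection 4 | 84 | none up to day 114 |

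**Step 2. Size.** Taps: 10 × 2 = 20. Taps at exit: 10 × 1 = 10. Share with no later scheduled check: 10/20 = 50%. The same count for injections is 10 of 10 × 4 = 40, or 25%, but injections are standard care and are secondary here. If fewer than 10 complete, each completer still has exactly one second tap without a later scheduled check.

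**Step 3. Does the 30-day window apply to completers?** The earlier-of wording raises the question whether exit at Week 12 counts as discontinuation or termination. Section 4.7 uses termination for stopping the whole study ("This study may be terminated by"). The subject discontinuation section describes withdrawal. Section 6.2 treats completion as a separate state ("before a study can be considered complete or terminated"), and section 5.6.2(f) likewise separates completing from discontinuing. The better reading is that a completer's window runs the full 30 days. The count in Step 1 does not depend on this, because nothing is scheduled after Week 12 on either reading.

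**Step 4. Order of tap and injection.** Section 4.8.3 places the second sample after the fourth injection, whereas sections 1.2, 3.1, 4.5.1 and the Safety Plan place it before. Both belong to Week 12, so the result is the same.

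**Step 5. With the fix.** One contact between day 85 and day 114 gives tap 2 a later scheduled check in every completer: 20 of 20 taps instead of 10 of 20.

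**The case against.** The strongest reply is that these patients are not lost. Section 4.8.3 commits the treating physicians to following all of them without condition; clinical need governs only the injections. Section 5.3 counts events however they come to light, including those the patient volunteers. Serious events and events of special interest are reportable to the manufacturer from the date of awareness (section 5.6.2(i)), and section 5.1 sends tap complications to the IRB with no stated end date. All of this stands. The gap is the absence of a scheduled study check, not the absence of care or of a reporting duty.

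A second reply is that a call or chart review cannot find mild intraocular inflammation, which needs a slit lamp. That also stands: the remedy captures symptoms and charted findings only. Nor is a 4-week examination after the first tap perfect, since an event may have resolved by then. The contrast between first and second taps is one of scheduled opportunity, not of certain detection.

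Three stronger readings are tempting, and the documents do not support them.
- *The AE window shuts on the day of exit.* The usage set out in Step 3 of the working points the other way. The wording is loose enough to be misread, but no more than that.
- *Tap injuries fall outside the causality system.* The *Yes* rule names the tap, and the examples under *No* (such as underlying disease or other medication) include no study procedure. A sensible investigator would answer *Yes*. A separate tap field would add little, because tap and injection occur at the same visit and could not be told apart. What remains is wording: the *No* rule and section 5.6.2(f) omit the tap.
- *The gap damages an estimate of tap risk.* No objective or outcome measure estimates a complication rate, and safety is only summarized, so limits on such a rate would inform no decision in this plan.

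**Conclusion.** The point holds as a low-cost improvement. Completers have no scheduled study AE contact in the 30 days after the Week 12 tap and injection, while early withdrawals do. With 10 completers this affects 10 of 20 taps (50%). The exposure is mainly to non-serious or delayed events. The primary VEGF and cytokine outcomes are not affected.

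The count assumes that all 10 patients complete and that Appendix A lists every scheduled contact. How many second taps routine care would in fact document is not given and could be anywhere from 0 to 10. The schedule gap itself is certain; its practical effect depends on that unknown number.

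**What to change.** **Main change (section 5.3 and Appendix A).** Add one AE contact for every completer within 30 days after the Week 12 tap and injection: a phone call plus a review of the routine-care chart, including any eye examination done in that period. State that the AE window for completers ends 30 days after the last tap or injection, and remove the earlier-of qualifier. Because tap and injection share a visit, the 30-day end date on the better reading does not move.

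**Minor wording.** Name the aqueous tap in the *No* causality rule of section 5.3 and in section 5.6.2(f).

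**Cost.** One flowchart column, a few sentences, and ten calls with chart checks. Database lock could be up to about 30 days later, with no added delay if the 30-day window is already being observed. Low-grade inflammation in an eye that nobody examines in that period would still be missed.
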